13.1 Prohibited Treatment

- Use of all non-study investigational medications or devices is prohibited during the 30 days prior to Screening through PTE.
- Systemic antibacterial agents potentially effective for ABSSSI are prohibited for 72 hours prior to randomization through PTE, except as rescue therapy in cases of clinical failure. A single dose of a short-acting potentially effective systemic antibacterial agent (see list in [Appendix 1](#)) administered within the 72 hours prior to randomization will be allowed for up to 25% of randomized subjects.
- Any topical antibacterial agent applied to the infection site with a spectrum that is active against the known or potential infecting pathogen(s) responsible for the infection under study within the 72 hours prior to randomization through PTE.
- MAO inhibitors. Linezolid is a reversible non-selective inhibitor of MAO. Therefore, subjects should not be enrolled who are either taking MAO inhibitors (eg, phenelzine, isocarboxazid), or have taken MAO inhibitors within 14 days prior to Screening. MAO inhibitors are prohibited from 14 days prior to Screening through the Final Follow-up assessment.
- Subjects will be instructed to avoid taking antacids and multivitamins containing multivalent cations (eg, aluminum, magnesium, calcium, bismuth, iron, or zinc) for 6 hours before and 4 hours after all odd numbered doses.

All other medications not prohibited by the protocol and considered necessary for the subject's welfare may be administered and/or continued under the supervision of the investigator.

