13.2.1 Dressings

Wounds may be covered with any sterile non-adherent type dressing (not containing any specific antibacterial agents) chosen by the investigator.

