13.2.2 Topical Solutions

Topical solutions with nonspecific activity such as povidone iodine can be used during dressing changes and as part of local care to lesions. However, solutions containing specific antibacterial agents (eg, mupirocin, retapamulin, fusidic acid) should not be used as part of the regimen involved in local infection site care.

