22.1 Analysis Populations

A number of subject analysis populations have been defined for the various analyses of efficacy and safety, as follows:

- The intent-to-treat (ITT) population will consist of all randomized subjects.

- The modified intent-to-treat (mITT) population will consist of all randomized subjects without a sole Gram-negative causative pathogen(s) at Screening.
- The clinically evaluable (CE) population will consist of all mITT subjects who received test article, have a qualifying ABSSSI, an assessment of outcome, and meet all other evaluability criteria detailed in the SAP.
- The microbiological modified intent-to-treat (micro-mITT) population will consist of subjects in the mITT population who have at least 1 Gram-positive causative pathogen(s) at Screening.
- The microbiologically evaluable (ME) population will include subjects in the CE population who have at least 1 Gram-positive causative pathogen(s) at Screening.
- The safety population will consist of all randomized subjects who receive test article.

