6.1.5.3 Concomitant Antibiotic Therapy

Subjects who receive any systemic concomitant antibiotic therapy from the first dose of test article through the EOT visit and through the PTE visit with a spectrum of activity against the known or potential Gram-positive infecting pathogen(s) responsible for the infection under study will be excluded from the CE-EOT and CE-PTE populations, respectively, unless the subject receives the antibiotic therapy for treatment of the ABSSSI due to insufficient therapeutic effect of the test article.

Subjects who receive a systemic concomitant antibiotic that is not effective against the Gram-positive baseline pathogen, or if no Gram-positive pathogen is isolated and the antibiotic does not have Gram-positive activity, will be included in the CE-EOT and CE-PTE populations.

In addition, subjects who have any topical antibacterial agent applied to the infection site (except for antibiotic/antiseptic-coated dressing applied to the clean postsurgical wound) with a spectrum

that is active against the known or potential infecting pathogen(s) responsible for the infection under study from the first dose of test article through the EOT or PTE visits, will be excluded from the CE-EOT and CE-PTE populations, respectively.

Antimicrobials that will not interfere with the course of the ABSSSI are allowed and do not affect inclusion in the CE populations, eg, metronidazole, norfloxacin, nalidixic acid, piperacillin sodium, oral vancomycin, antifungals, antivirals or topical antibiotics used for decontamination or in places other than the primary lesion.

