7 CHANGES IN CONDUCT OR PLANNED ANALYSES FROM THE PROTOCOL

There are no changes to the analyses as detailed in the protocol.

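### The CE rule in SAP 6.1.5.3 keeps subjects with an antibiotic-coated dressing on a clean postsurgical wound at the infection site, a dressing that protocol 13.1 and 13.2.1 do not allow

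*SAP*

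**What the plan says.** **Protocol, conduct at the site.** Section 13.1 prohibits topical antibacterials with relevant activity at the infection site from 72 hours before randomization through PTE. Section 13.2.1 says of dressings: "Wounds may be covered with any sterile non-adherent type dressing (not containing any specific antibacterial agents) chosen by the investigator". Section 13.2.2 separates two kinds of solution. On nonspecific agents it says "Topical solutions with nonspecific activity such as povidone iodine can be used during dressing changes". Solutions with specific antibacterial agents "should not be used as part of the regimen involved in local infection site care". None of the three sections has an exception for a clean postsurgical wound.

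**SAP, evaluability.** Section 6.1.5.3 starts from nearly the same bar as protocol 13.1: "In addition, subjects who have any topical antibacterial agent applied to the infection site" with relevant activity, between first dose and EOT or PTE, leave CE-EOT or CE-PTE respectively. It then inserts the exception "except for antibiotic/antiseptic-coated dressing applied to the clean postsurgical wound". Later in the same section it separately exempts topical antibiotics used for decontamination or away from the primary lesion.

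**How the documents connect.** Protocol 22.1 requires CE subjects to "meet all other evaluability criteria detailed in the SAP", so the detailed criteria are left to the SAP. SAP Section 7 says: "There are no changes to the analyses as detailed in the protocol".

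**The concern.** The SAP takes over the protocol's bar on active topical antibacterials and then exempts one use that the protocol forbids. The same subject can be recorded under SAP 13.1 as a deviation for prohibited treatment and still count as evaluable.

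The situation is foreseeable. Protocol 13.2.3 regards adjunct surgery as needed in many of these infections and allows planned procedures up to 48 hours after the start of test article. Major abscess may make up 30% of randomized subjects (0.30 × 704 ≈ 211). SAP 6.1.5.4 generally keeps subjects with minor bedside procedures in CE.

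What is at stake is the meaning of the CE and ME results. The topical rule exists so that success in these populations can be read as response to test article. For the EMA, protocol 22.4.3 requires non-inferiority in both mITT and CE. If active local treatment were used in both arms it could pull the success rates together, which is the unfavourable direction for a non-inferiority comparison.

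**Working it through.** The issue is textual, so the passages are compared first. The power figures then show what the remedy would cost.

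**Step 1. Compare the rules for a clean postsurgical wound at the infection site.**

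| Item on the wound | Protocol | SAP 6.1.5.3 | Agreement |
|---|---|---|---|
| Nonspecific antiseptic | Allowed as a solution in local care (13.2.2); 13.2.1 bars only specific antibacterials in dressings | Antiseptic-coated dressing does not exclude from CE | Broadly yes |
| Dressing coated with an antibiotic active against the pathogen | Not allowed (13.1, 13.2.1) | Does not exclude from CE | No |
| Any other active topical antibacterial | Not allowed (13.1, 13.2.2) | Excludes from CE, apart from use for decontamination | Yes, apart from that use |

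Only the middle row conflicts.

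**Step 2. Does the exception operate at the lesion under study?** Yes. It sits inside a clause limited to agents applied to the infection site. Use away from the primary lesion has its own exemption, so this one would have nothing to do unless the wound is at the infection site.

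**Step 3. Which analyses does it reach?**
- Early Clinical Response in mITT (SAP 10.1): not affected, because the exception is a CE criterion.
- CE-EOT and CE-PTE: affected. SAP 10.3 and 10.4 treat their confidence intervals as descriptive and draw no non-inferiority conclusion from them.
- ME-EOT and ME-PTE: affected, because SAP 6.1.6 forms them from CE and micro-mITT.
- EMA primary analysis: CE is co-primary with mITT (protocol 22.4.3). Whether the EMA SAP has the same exception cannot be seen.

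**Step 4. Reproduce the plan's CE power.** Inputs from protocol 22.13 and SAP 5.1.1: 704 × 0.80 = 563.2, given as 564, so n = 282 per arm; success 90% in both arms; margin 0.10; one-sided alpha 0.025.

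Farrington-Manning power = Φ[(0.10 − 1.96 × s0) / s1], where
- s1 = √(2 × 0.90 × 0.10 / 282) = 0.02526;
- s0 uses the rates fitted under a true difference of −0.10, which are 0.8313 and 0.9313: s0 = √[(0.8313 × 0.1687 + 0.9313 × 0.0687) / 282] = 0.02691.

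Power = Φ[(0.10 − 0.05274) / 0.02526] = Φ(1.87) = 96.9%. The plan states 97%, so the figure reproduces.

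**Step 5. Power if the antibiotic exception is removed.** The share of CE subjects with such a dressing is not in the documents. The shares below are assumptions, with n per arm = 282 × (1 − share), rounded down.

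| Assumed share leaving CE | CE subjects left | Power |
|---|---|---|
| 1% | 558 | 96.8% |
| 2% | 552 | 96.6% |
| 5% | 534 | 96.1% |
| 10% | 506 | 95.2% |

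**Step 6. Weight of one subject.** One subject is 1/282 = 0.35 percentage points of an arm's CE success rate. This moves the treatment difference only if the dressing changes that subject's outcome, or if keeping such subjects falls unevenly on the arms.

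**The case against.** The strongest reply is that prohibited treatment and non-evaluability are separate questions. The protocol sections govern conduct at the site. Protocol 22.1 leaves the CE criteria to the SAP, and a SAP may keep a subject whose deviation it judges not to confound the outcome. The deviation is not hidden, because SAP 13.1 lists prohibited treatments as a category, graded major or minor before unblinding. This stands to the extent that keeping such a subject is not automatically an error. It does not explain why the SAP adopts the protocol's bar and then reverses part of it without a reason.

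A reader might also infer more than the documents support:
- *That every antibiotic-coated dressing on the infection site is exempt.* The exception is confined to the clean postsurgical wound. Such dressings elsewhere on the lesion still exclude.
- *That SAP Section 7 is false.* It speaks of analyses detailed in the protocol, and the protocol details no analysis rule for dressings. The mismatch is between a conduct rule and an evaluability criterion.
- *That CE is meant to contain no other antibacterial treatment.* SAP 6.1.5.3 keeps subjects given rescue antibiotics for insufficient effect and those given topical antibiotics for decontamination.
- *That success is inflated and the arms are drawn together.* Nothing in the documents shows that such a dressing changes the PTE outcome in a subject already on active systemic therapy. The effect is possible but not demonstrated.
- *That a countable number of CE outcomes is confounded.* No frequency is given, and a dressed wound is not in itself a changed outcome.

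**Conclusion.** The inconsistency is real and narrow. On the current text, a subject with an antibiotic-coated dressing on a clean postsurgical wound at the infection site has had treatment that the protocol prohibits, yet remains in CE and, if also in micro-mITT, in ME. The antiseptic half of the exception raises no issue.

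The consequence is minor. It concerns what the CE and ME populations represent, not sample size or power. It could bear on a confirmatory conclusion only through the EMA co-primary CE analysis, and only if the EMA SAP carries the same exception. Even there, non-inferiority must also be shown in mITT, which the exception does not touch. The size and direction of any bias cannot be determined from the documents. The power range rests on assumed shares of 1% to 10% and on the plan's own 90% success rate in both arms. Which dressing rule is clinically right is not judged here.

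**What to change.** Reconcile SAP 6.1.5.3 with protocol 13.1, 13.2.1 and 13.2.2 before unblinding, while evaluability is still being settled blind under SAP 6.2.2. As long as the protocol text stands, limit the CE exception to antiseptic-coated dressings by deleting the reference to antibiotic coating. An antibiotic-coated dressing active against the pathogen is then handled like any other topical antibacterial on the infection site. If the sponsor prefers to keep the antibiotic exception, the SAP should state it openly as a departure from the protocol's conduct rule and justify it. Check the EMA SAP for the same wording.

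The cost is a small deletion in the SAP and possibly a few subjects leaving CE and ME. CE power stays at about 95% or more across the assumed range.

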6.1.5.4 Concomitant Surgical Procedures

Subjects who receive an unplanned major surgical procedure for the infection under study (ie, procedures that would not normally be performed at the bedside, such as amputation or major incision and drainage performed in an operating room) will be defined as a clinical failure for the clinical response at the EOT and PTE Visits and thus, will be included in the CE populations.

Minor bedside procedures such as debridement, aspiration puncture, excision with or without skin grafting and wound cleaning/lavage will generally be acceptable and will not exclude a subject from the CE populations. All other surgical procedures performed after the first dose of test article will be reviewed by the Sponsor to determine whether the procedure potentially confounds the outcome and whether the subject should be excluded from either the CE-EOT or CE-PTE populations.

6.1.5.5 Test Article Therapy

Subjects must meet all of the following to be included in the CE populations:

- Received test article and the correct test article based on the randomization assignment
- Study personnel involved in the assessment of efficacy remained blinded to study treatment, unless a treatment limiting adverse event occurred which required emergency unblinding.
- Subject was at least 80% compliant with the dosing regimen.
- Evaluable failure: The subject received at least 2 doses of active test article (omadacycline group) or at least 4 doses of active test article (linezolid group) and the investigator classifies the subject as a Clinical Failure at the EOT Visit (CE-EOT population) or the overall Clinical Response (based on the investigator's assessment) at the PTE Visit (CE-PTE population) is Clinical Failure.
- Evaluable success: The subject received at least 3 doses of active test article (omadacycline group) or at least 6 doses of active test article (linezolid group) and the investigator classifies the subject as a Clinical Success at the EOT Visit (CE-EOT population) or the overall Clinical Response (based on the investigator's assessment) at the PTE Visit (CE-PTE population) is Clinical Success.

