- ^{aa} Subjects should be instructed not to take the odd numbered dose on Day 3 until they return to the site for the Day 3 visit.
- ^{bb} At selected sites, subjects who have agreed to participate in PK evaluation and have signed a separate PK evaluation consent form will have up to 4 blood samples collected between Days 2 and 3. The PK sample collection schedule for the individual subject will be provided by the Sponsor.
- ^{cc} At the investigator's discretion, all therapy may be discontinued after the 7th day of treatment, when the infection is considered clinically cured (based on normalization of the clinical signs and symptoms of infection and the investigator's clinical assessment that continued systemic antibacterial therapy is no longer needed).

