14.3.1.1 Treatment Phase

The study will employ a double-blind, double-dummy design using omadacycline placebo comparator tablets of matching size and shape to active omadacycline tablets and matching over-encapsulated placebo and over-encapsulated active linezolid tablets. To maintain investigator and subject blinding, subjects on both arms will receive the same number of tablets as shown in [Table 1](#).

All doses of test article should be taken with water. There are fasting requirements for administration of the odd numbered doses due to effects of food on oral omadacycline (see [Table 1](#)). These fasting requirements should be considered when determining the time of day when subjects will take their doses.

In order to perform protocol-required procedures, Dose 1 and the odd numbered doses on Days 2 and 3 should be taken at the site. Ability to perform the study procedures and the fasting requirements for the odd numbered doses should be considered when determining when subjects visit the clinic on Days 2 and 3.

On Day 1, Dose 1 will be administered after the completion of all required Screening and Day 1 procedures and within 4 hours after randomization as outlined in [Section 8](#). On Day 1, a second dose should be taken provided that 1) it can occur a minimum of 8 hours after Dose 1, and 2) it can occur a minimum of 8 hours before the expected time of the next dose (ie, Dose 3); otherwise only Dose 1 should be taken that day. Starting on Day 2, test article will be taken twice daily, with approximately 12 hours (at least 8 hours) separating each dose.

Table 1. Treatment Regimens for Oral Test Article

Dosing		Omadacycline Arm	Linezolid Arm	Dosing Condition
Day 1	Dose 1	Three 150 mg omadacycline tablets and one over-encapsulated placebo tablet resembling linezolid	Three placebo tablets resembling omadacycline and one over-encapsulated 600 mg linezolid tablet	Fasting ^a
	Dose 2 ^b	One over-encapsulated placebo tablet resembling linezolid	One over-encapsulated 600 mg linezolid tablet	No restrictions
Day 2	Dose 3	Three 150 mg omadacycline tablets and one over-encapsulated placebo tablet resembling linezolid	Three placebo tablets resembling omadacycline and one over-encapsulated 600 mg linezolid tablet	Fasting ^a
	Dose 4	One over-encapsulated placebo tablet resembling linezolid	One over-encapsulated 600 mg linezolid tablet	No restrictions

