Day 3 and all subsequent study days	Dose 5 and odd doses	Two 150 mg omadacycline tablets and one over-encapsulated placebo tablet resembling linezolid	Two placebo tablets resembling omadacycline and one over-encapsulated 600 mg linezolid tablet	Fasting ^a
	Dose 6 and even doses	One over-encapsulated placebo tablet resembling linezolid	One over-encapsulated 600 mg linezolid tablet	No restrictions

a Fasting: no food, antacids or multivitamins containing multivalent cations (eg, aluminum, magnesium, calcium, bismuth, iron, or zinc) or drink except water for at least 6 hours before dosing; after dosing, no food for 2 hours, no dairy products, antacids or multivitamins containing multivalent cations (eg, aluminum, magnesium, calcium, bismuth, iron, or zinc) for 4 hours

b On Day 1, Dose 2 should be taken provided that 1) it can occur a minimum of 8 hours after Dose 1 and 2) it can occur a minimum of 8 hours before the expected time of the next dose (ie, Dose 3); otherwise Dose 2 should be skipped.

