9.3 Treatment Compliance and Exposure

Exposure summary by treatment group will be presented for the Safety, mITT, and CE-PTE populations. The distribution of subjects by the total number of days on therapy (1 to 3, 4 to 6, 7 to 10, 11 to 12, 13 to 14 and > 14 days) will be presented as will descriptive statistics for the total number of days on therapy.

Treatment compliance is defined as the number of active tablets actually received divided by the number of active tablets expected ($\times 100$) over the time period defined by the first and last dose date. The last dose date is the last day the subject is expected to receive test article based on the length of therapy determined by the Investigator or the actual last date the subject took test article, if s/he prematurely discontinued test article due to treatment failure or an adverse event. Dose 2 can be missed per protocol if it cannot be taken a minimum of 8 hours after Dose 1 and a minimum of 8 hours before the expected time of Dose 3. Descriptive statistics for treatment

compliance and the number and percentage of subjects at least 80% compliant will be presented by treatment group for the mITT and Safety populations.

A summary of compliance with the pre- and post-dose fasting requirements will also be provided. The percent fasting compliance will be determined based on the total doses taken where fasting is required. The percentage of subjects who were < 50%, 50% to < 80%, and 80% to 100% compliance with the pre-dose and post-dose fasting requirements will be summarized for the mITT and Safety populations.

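### If Dose 2 is skipped as the protocol directs, a failure ending at Dose 4 stays in the CE population on omadacycline but is dropped on linezolid

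*SAP*

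**What the plan says.** SAP 6.1.5.5 lists conditions that must all be met for the CE populations. One is compliance: "Subject was at least 80% compliant with the dosing regimen". Two others are minimum counts of active doses. An evaluable failure needs "at least 2 doses of active test article (omadacycline group) or at least 4 doses of active test article (linezolid group"; an evaluable success needs "at least 3 doses of active test article (omadacycline group) or at least 6 doses of active test article (linezolid group". The section makes no allowance for a missed Dose 2.

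Protocol 14.3.1.1 requires Dose 2 to be at least 8 hours after Dose 1 and at least 8 hours before Dose 3. Table 1 note b gives the second condition and the consequence: "it can occur a minimum of 8 hours before the expected time of the next dose (ie, Dose 3); otherwise Dose 2 should be skipped". Later doses keep their numbers. In Table 1, even-numbered doses are placebo only on omadacycline and one active 600 mg tablet on linezolid.

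SAP 9.3 defines compliance as the "number of active tablets actually received divided by the number of active tablets expected", expressed as a percentage. Within that definition it adds that "Dose 2 can be missed per protocol if it cannot be taken a minimum of 8 hours after Dose 1" and before Dose 3. It does not say in terms that the skipped tablet leaves the expected count.

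Under SAP 6.2.2, criteria that need the actual treatment are applied programmatically after unblinding.

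**The concern.** The paired minimums look designed to mean the same stretch of treatment in both arms: two dosing days for a failure, three for a success. A skipped Dose 2 breaks that match, because the tablet is active in one arm only. Two subjects who both followed the protocol, both skipped Dose 2 as told, and both failed with Dose 4 as their last dose are then classified differently by arm.

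Such a stop is plausible. Dose 5 waits for a clinic visit: "Subjects should be instructed not to take the odd numbered dose on Day 3 until they return to the site for the Day 3 visit". Protocol 14.3.1.2 has the investigator decide at visits whether to continue or discontinue. The documents do not say how often stops fall there.

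What is at stake is the make-up of the CE population. CE-PTE is descriptive in this SAP (10.3). Protocol 22.4.3 makes CE co-primary with mITT for the EMA.

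**Working it through.** **1. Active doses by last scheduled dose.** From Table 1, with L the number of the last dose taken (L at least 2) and every earlier dose taken except possibly Dose 2:

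- omadacycline = number of odd doses up to L
- linezolid = L if Dose 2 was taken, L − 1 if it was skipped

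| Last dose | Omadacycline | Linezolid, Dose 2 taken | Linezolid, Dose 2 skipped |
|---|---|---|---|
| 3 | 2 | 3 | 2 |
| 4 | 2 | 4 | 3 |
| 5 | 3 | 5 | 4 |
| 6 | 3 | 6 | 5 |
| 7 | 4 | 7 | 6 |

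With Dose 2 taken, the Dose 4 row gives 2/4 and the Dose 6 row gives 3/6. These are the SAP minimums exactly.

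**2. When each minimum is first met.**

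| | Omadacycline (either case) | Linezolid, Dose 2 taken | Linezolid, Dose 2 skipped |
|---|---|---|---|
| Failure (2/4) | Dose 3 | Dose 4 | Dose 5 |
| Success (3/6) | Dose 5 | Dose 6 | Dose 7 |

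A one-dose gap between arms exists even without a skip: a failure ending at Dose 3 has 2 active doses on omadacycline (kept) and 3 on linezolid (excluded). The skip widens the gap to two scheduled doses. The added case is the failure ending at Dose 4: 2 against a minimum of 2, and 3 against a minimum of 4.

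**3. Compliance for the same subject.** If the skipped Dose 2 were counted as expected, linezolid compliance through Dose 4 would be 3/4 = 75%, below 80%. Omadacycline would be 6/6 active tablets = 100%. If it is not counted, linezolid is 3/3 = 100%.

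**4. Number affected.** The plan has 564 CE subjects, or 282 per arm. At the assumed 90% success rate, 0.90 × 282 = 253.8, taken as 254 successes and 28 failures per arm. The documents give neither the share who skip Dose 2 nor the share of failures ending at Dose 4, so both are assumptions:

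- low: 28 × 0.05 × 0.05 = 0.07
- middle: 28 × 0.25 × 0.10 = 0.7
- high: 28 × 0.50 × 0.20 = 2.8

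**5. Effect on the CE result.** The power formula is Φ[(p₁ − p₂ + 0.10 − 1.96·s₀)/s₁]. Here s₀ is the standard error under the Farrington-Manning restriction to a difference of −0.10, and s₁ is the unrestricted one. It first reproduces the plan: 90.0% at 79% with 704, 95.6% at 85% with 704, and 96.9% at 90% with 564, against the stated 90%, 96% and 97%.

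Next, k linezolid failures are removed: omadacycline 254/282 against linezolid 254/(282 − k). The lower limit is the Miettinen-Nurminen root in SAP 10.1.

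| k | Linezolid rate | Shift (points) | Lower limit (points) | Power |
|---|---|---|---|---|
| 0 | 90.07% | 0 | −5.04 | 97.0% |
| 1 | 90.39% | +0.32 | −5.34 | 96.2% |
| 2 | 90.71% | +0.64 | −5.63 | 95.3% |
| 3 | 91.04% | +0.97 | −5.93 | 94.2% |

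One excluded linezolid success changes its rate by 253/281 − 254/282 = −0.04 points. With at least 7 days of planned therapy, a success ending by Dose 6 should be rare.

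**The case against.** The best defence is that the rule measures exposure. SAP 6.1.5.5 treats compliance separately and counts active doses. Two once-daily omadacycline doses and four twice-daily linezolid doses are each two days of drug. A linezolid subject who skips Dose 2 and ends at Dose 4 has had three doses, or a day and a half. Excluding that subject then reflects less drug received. This reading is possible, and the documents do not state the rule's purpose. It does not remove the point: the rule still drops failures who followed the protocol from one arm only, because of a dose that is placebo in the other.

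Several stronger readings are tempting and are not supported:

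- That every linezolid failure ending at Dose 4 is excluded. With Dose 2 taken, such a subject has 4 active doses and meets the minimum.
- That the subject also fails the 80% rule. The sentence on Dose 2 sits inside the compliance definition in SAP 9.3 and is most naturally read as excusing the skip. The 75% figure arises only if it has no effect. That allowance, however, does not reach the separate dose minimum.
- That the rule helps omadacycline. Removing linezolid failures raises the linezolid rate, which works against omadacycline.
- That applying the count after unblinding invites manipulation. The minimum is fixed in advance and applied by program. The risk would lie in adding an exception once treatment is known.

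It is also fair that lowering the linezolid minimum to 3 and 5 does not give full symmetry: a failure ending at Dose 3 would still be kept on omadacycline and excluded on linezolid.

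**Conclusion.** The concern holds for subjects who skip Dose 2 under Table 1 note b. The fixed minimums then no longer correspond to the same scheduled dose in the two arms, and nothing else in the SAP corrects this.

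It is minor. The middle assumption gives 0.7 of a subject and the assumed range is 0.07 to 2.8, so three exclusions lie just beyond it. These figures rest on the planned CE size and success rate, on assumed skip and stop shares that have no source in the documents, and on the other CE criteria being met. The success minimum hardly matters.

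A reader might infer a threat to the trial's conclusion. The documents do not show one. The FDA primary analysis uses Early Clinical Response in mITT, and no non-inferiority conclusion is drawn from CE-PTE in this SAP. A confirmatory effect would require the EMA SAP to repeat the rule, which cannot be checked here.

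**What to change.** Preferred: in SAP 6.1.5.5, state the minimum by scheduled dose for both arms. For example: *test article taken through at least Dose 4 for an evaluable failure and Dose 6 for an evaluable success; a Dose 2 skipped under protocol Table 1 note b is allowed.* This also removes the remaining asymmetry at Doses 3 and 5, and this criterion can then be applied before unblinding. It tightens omadacycline by one placebo dose: a failure ending at Dose 3, now kept, would be excluded.

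Narrower alternative: keep the active-dose counts, and set the linezolid minimum to 3 (failure) and 5 (success) when Dose 2 was skipped under note b. This restores the Dose 4 and Dose 6 cut-offs on linezolid but leaves the asymmetry at Doses 3 and 5.

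With either, clarify in SAP 9.3 that a permitted Dose 2 skip is not an expected tablet, and use the same wording in the EMA SAP if it repeats the rule. Both options move CE slightly towards omadacycline, so the choice should be made before unblinding.

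The cost is two SAP sentences. No new data are needed, because the test article eCRF already carries reconciled dosing information (protocol 15.4), and the protocol need not change.
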